---

## LIST OF ABBREVIATIONS

AE	adverse event
AED	antiepileptic drug
BCR	borderline or clinical range
BMI	body mass index
BRIEF ®	Behavior Rating Inventory of Executive Function ®
BRIEF ® -P	Behavior Rating Inventory of Executive Function ® - Preschool Version
C-SSRS	Columbia-Suicide Severity Rating Scale
CBCL	Child Behavior Checklist
COVID-19	coronavirus disease 2019
CRF	Case Report Form
CV	coefficient of variance
DBP	diastolic blood pressure
DRM	Data Review Meeting
ECG	electrocardiogram
eCRF	electronic Case Report Form
ER	emergency room
ETV	Early Termination Visit
FAS	Full Analysis Set
HRQoL	health-related quality of life
IIL	Initiating intravenous lacosamide Group
ILAE	International League Against Epilepsy
LCM	Lacosamide
MA	markedly abnormal

---

MedDRA	Medical Dictionary for Regulatory Activities
OLL	Open-label lacosamide Group
PDILI	Potential Drug Induced Liver Injury
PedsQL	Pediatric Quality of Life Inventory
PK	pharmacokinetic
PK-PPS	Pharmacokinetic Per-Protocol Set
PT	preferred term
RxL	Prescription lacosamide (eg, VIMPAT) Group
SAE	serious adverse event
SAP	Statistical Analysis Plan
SBP	systolic blood pressure
SD	standard deviation
SOC	system organ class
SPD	Specification of Protocol Deviations
SS	Safety Set
TEAE	treatment-emergent adverse event
TEMA	treatment-emergent markedly abnormal
ULN	upper limit of normal
VNS	vagus nerve stimulation
WHOCD	World Health Organization Drug Dictionary

## 1 INTRODUCTION

This Statistical Analysis Plan (SAP) defines the scope of statistical analyses and provides a detailed description of statistical methodology for the statistical analyses to support the final clinical study report for SP848.

## 2 PROTOCOL SUMMARY

### 2.1 Study objectives

The objectives of this study are:

- To obtain information about the safety, tolerability, and pharmacokinetic (PK) of Lacosamide (LCM) during long-term exposure
- To obtain preliminary efficacy data on seizure frequency during long-term exposure
- To allow study participants who have participated in SP847 (or discontinued SP847 due to a dose reduction or status epilepticus) to continue receiving LCM
- To allow study participants who have participated in other LCM pediatric clinical studies in epilepsy to continue receiving LCM
- Beginning with Protocol Amendment 4, at selected sites, to allow up to approximately 100 eligible pediatric study participants  $\geq 4$  years to  $\leq 17$  years of age who have not previously received LCM to begin receiving LCM

### 2.2 Study variables

### 2.3 Safety variables

#### 2.3.1 Primary safety variables

The primary safety variables are as follows:

- Incidence of Treatment Emergent Adverse events (TEAEs)
- Incidence of Serious Adverse Events (SAEs)
- Subject withdrawal from the study due to TEAEs

#### 2.3.2 Other safety variables

The other safety variables are:

- Hematology, blood chemistry, endocrinology, and urinalysis parameters
- 12-lead electrocardiograms (ECGs)
- Vital sign measurements (blood pressure and pulse)
- Physical and neurological examination findings
- Body weight, height, and calculated body mass index (BMI)
- Tanner Stage (if applicable)
- Achenbach Child Behavior Checklist (CBCL) for children 18 months and older (CBCL/1½-5 and CBCL/6-18) assessing behavior

- Bayley-III scales for children <18 months of age at time of enrollment (applicable only to study participants enrolled in English-speaking countries)
  - Cognitive function assessments (Behavior Rating Inventory of Executive Function – Preschool Version [BRIEF-P]/ Behavior Rating Inventory of Executive Function [BRIEF]) (if applicable) for children  $\geq 2$  years of age
- LCM palatability and ease of use questionnaire.

### **2.3.3 Pharmacokinetic variables**

#### **2.3.3.1 Primary Pharmacokinetic variables**

No primary PK variables are defined for this study.

#### **2.3.3.2 Other Pharmacokinetic variables**

The other PK variables are:

- Plasma concentration of LCM (for population PK analysis) and concomitant antiepileptic drugs (AEDs)

### **2.3.4 Efficacy variables**

#### **2.3.4.1 Primary efficacy variables**

No primary efficacy variables are defined for this study.

#### **2.3.4.2 Secondary efficacy variables**

The secondary efficacy variables, based on daily seizure diaries are:

- Percent change from Baseline in 28-day partial-onset seizure frequency
- $\geq 50\%$  reduction in 28-day partial-onset seizure frequency
- $\geq 75\%$  reduction in 28-day partial-onset seizure frequency
- Seizure days per 28 days (subjects with generalized seizures only)
- Seizure-free status

#### **2.3.4.3 Other efficacy variables**

The other efficacy variables are:

- Clinical Global Impression of Change
- Caregiver Global Impression of Change
- Quality of life assessments (Pediatric Quality of Life Inventory [PedsQL™]) (if applicable)
- Health care resource use (concomitant AEDs, medical procedures, health care provider consultations not related to study, hospitalizations not related to study)
- All seizure frequency analyses as described in secondary efficacy variables (presented for the overall Treatment Period only) may be additionally presented by modal daily dose group, by seizure type, by seizure classification subgroup, by time interval, by visit or time period, or by completer cohort.

## **2.4 Study design and conduct**

### **2.4.1 Study description**

#### **2.4.1.1 Study participants enrolling from SP847 or other LCM pediatric clinical studies in epilepsy (rollover study participants)**

Study participants who complete SP847 (including discontinuation from SP847 due to a dose reduction or status epilepticus) or study participants from another applicable LCM pediatric clinical study in epilepsy and who choose to enter the open-label study (rollover study participants), will begin on the LCM dose that they were receiving at the end of the previous pediatric study. Study participants will be able to continue on LCM oral solution (syrup) or switch to LCM tablets. During the study, investigators will be allowed to increase or decrease the dose of LCM and/or concomitant AEDs to optimize tolerability and seizure reduction for each subject. The investigator may adjust the LCM dose to a minimum of 2mg/kg/day (oral solution [syrup]) or 100mg/day (tablet) and a maximum of 12mg/kg/day (oral solution [syrup]) or the corresponding dose levels for the tablet formulation), not to exceed 600mg/day based on body weight, even if the subject's body weight exceeds 50kg. The maximum permitted LCM dose in SP848 is 12mg/kg/day or 600mg/day, whichever is lower. Increases in the LCM dose must occur only during office visits. If needed to optimize tolerability and seizure reduction in selected study participants, concomitant AEDs may be carefully tapered and discontinued to achieve LCM monotherapy. New concomitant AEDs may be introduced as treatment if the medication has been approved by the Regulatory Authorities in the country in which the subject lives. New concomitant AEDs should be added only when the subject has not optimally or adequately responded to a maximum tolerated dose of LCM. When study participants are withdrawn from the study, it is recommended that LCM be tapered gradually in weekly decrements of 4mg/kg/day (oral solution [syrup]) or 200mg/day (tablets) for study participants who have achieved a dose of LCM  $\geq 6$ mg/kg/day (oral solution [syrup]) or  $\geq 300$ mg/day (tablet). A slower taper in weekly decrements of 2mg/kg/day (oral solution [syrup]) or 100mg/day (tablets) is permitted, if medically necessary. In case of an emergency, a faster taper is permitted after discussion with the medical monitor, whenever possible.

#### **2.4.1.2 Study participants enrolling directly into SP848**

Beginning with Protocol Amendment 4, at selected sites, up to approximately 100 eligible pediatric study participants  $\geq 4$  years to  $\leq 17$  years of age with partial-onset seizures (deemed appropriate for treatment with adjunctive LCM) who have not previously received LCM will be permitted to enroll directly into SP848.

Beginning with local Protocol Amendment 5.2 for sites in Japan, approximately 46 eligible pediatric subjects  $\geq 4$  years to  $\leq 17$  years of age with partial-onset seizures who have not previously received LCM will be permitted to directly enroll at approximately 9 sites in Japan. Beginning with Protocol Amendment 5.4 for sites in China, approximately 60 additional eligible pediatric subjects with partial-onset seizures aged  $\geq 4$  years to  $\leq 17$  years, who have not previously participated in a LCM clinical study, will directly enroll into SP848.

Subjects who enroll directly into SP848 without previous participation in a LCM clinical study will undergo screening. Eligible subjects will initiate treatment with LCM, and the LCM dose will be titrated to a level to optimize tolerability and seizure control. Subjects will be able to

receive LCM oral solution or LCM tablets for up to 2 years as determined appropriate by the investigator.

SP848 includes subjects  $\geq 1$  month to  $\leq 18$  years of age since subjects who complete SP847 or another applicable LCM pediatric epilepsy study in subjects  $< 18$  years of age may have aged to 18 years old by the time they complete that study and enroll in SP848.

The same study conditions described in Section 2.4.1.1 (e.g., minimum and maximum LCM dose, required office visits for dose increases, concomitant AEDs, and LCM taper) also apply.

## 2.4.2 Tabular schedule of study procedures

The schedule of the study procedures for SP848 are provided in Section 16.1 of the study protocol and country specific protocol amendments for Japan and China.

## 2.5 Determination of sample size

Approximately 42 study participants from the SP847 study will be eligible to enroll in this open-label study. Other subjects will be eligible to enroll as other LCM pediatric clinical studies in epilepsy are undertaken.

In addition, at selected sites, beginning with Protocol Amendment 4, up to approximately 100 eligible pediatric study participants  $\geq 4$  years to  $\leq 17$  years of age who have not previously participated in a LCM clinical study will be permitted to enroll directly into SP848. Beginning with local Protocol Amendment 5.2 for sites in Japan, approximately 46 eligible pediatric subjects  $\geq 4$  years to  $\leq 17$  years of age with partial-onset seizures who have not previously received LCM will directly enroll at approximately 9 sites in Japan. Beginning with local Protocol Amendment 5.4 for sites in China, approximately 60 additional eligible pediatric subjects with partial-onset seizures aged  $\geq 4$  years to  $\leq 17$  years, who have not previously participated in a LCM clinical study, will enroll directly into SP848. The purpose of enrolling these subjects directly into SP848 is to obtain additional long-term safety exposures in the age range from which adequate PK data have already been obtained in SP847; the additional long-term safety data will be included in planned LCM marketing applications for study participants  $\geq 4$  years of age.

Beginning with Protocol Amendment 6, up to 75 eligible pediatric subjects  $\geq 4$  years to  $< 17$  years of age who have participated in EP0060 will be permitted to enroll into SP848. Protocol Amendment 8 allows an enrollment increase from 75 to 100 eligible pediatric subjects  $\geq 1$  month to  $\leq 17$  years of age with epilepsy who participated in EP0060 to enroll in SP848 in order to reflect EP0060's inclusion of subjects down to 1 month of age.

In total, up to approximately 400 subjects may be eligible to participate in SP848.

## 3 DATA ANALYSIS CONSIDERATIONS

### 3.1 General presentation of summaries and analyses

Statistical analysis and generation of tables, figures, subject data listings, and statistical output will be performed using SAS Version 9.1 or higher. All tables and listings will use Courier New font size 9.

Descriptive statistics will be displayed to provide an overview of the study results. For categorical parameters, the number and percentage of study participants in each category will be

presented. The denominator for percentages will be based on the number of study participants appropriate for the purpose of analysis. Unless otherwise noted, all percentages will be displayed to 1 decimal place. No percentage will be displayed for zero counts, and no decimal will be presented when the percentage is 100%. For continuous parameters, descriptive statistics will include number of study participants (n), mean, standard deviation (SD), median, minimum, and maximum.

Decimal places for descriptive statistics will always apply the following rules:

- “n” will be an integer
- Mean, SD, and median will use 1 additional decimal place compared to the original data
- Coefficient of variance (CV[%]) will be presented with 1 decimal place
- Minimum and maximum will have the same number of decimal places as the original value

All summaries, unless otherwise stated below, will be presented overall for all study participants and additionally based on the subject’s age at time of entry into study SP848, using the following age groups:

- $\geq 1$  month to  $< 4$  years
- $\geq 4$  to  $< 18$  years
- Total  $\geq 1$  month to  $< 18$  years
- $\geq 18$  years
- All subjects

Summaries for PedsQL will be presented overall for all applicable study participants and additionally based on the subject’s age at Baseline (using the Baseline definition in Section 3.3), using the following age groups:

- $\geq 1$  month to  $\leq 12$  months
- $> 12$  months to  $\leq 24$  months
- $> 2$  years to  $\leq 4$  years
- $\geq 5$  to  $\leq 7$  years
- $\geq 8$  to  $\leq 12$  years
- $\geq 13$  to  $\leq 18$  years
- Total  $\geq 5$  years to  $\leq 18$  years

Summaries for CBCL/1½-5 will be presented overall for all applicable study participants and additionally based on the subject’s age at time of entry into study SP848, using the following age groups:

- $\geq 18$  months to  $< 2$  years
- $\geq 2$  to  $< 4$  years
- Total  $< 4$  years

- $\geq 4$  to  $< 6$  years

Summaries for CBCL 6-18 will be presented overall for all applicable study participants and additionally based on the subject's age at time of entry into study SP848, using the following age groups:

- $\geq 6$  to  $< 12$  years
- $\geq 12$  to  $< 16$  years
- Total  $\geq 6$  to  $< 16$  years
- $\geq 16$  years

Summaries for BRIEF-P will be presented overall for all applicable study participants and additionally based on the subject's age at time of entry into study SP848, using the following age groups:

- $\geq 2$  to  $< 4$  years
- $\geq 4$  to  $< 5$  years

Summaries for BRIEF will be presented overall for all applicable study participants and additionally based on the subject's age at time of entry into study SP848, using the following age groups:

- $\geq 5$  to  $< 12$  years
- $\geq 12$  to  $< 16$  years
- Total  $\geq 5$  to  $< 16$  years
- $\geq 16$  years

Summaries for Bayley-III assessments will be presented overall for all applicable study participants and additionally based on the subject's age at time of entry into study SP848, using the following age groups:

- $\geq 1$  to  $< 6$  months
- $\geq 6$  months to  $< 1$  year
- $\geq 1$  year to  $< 18$  months

All summaries will be descriptive; no statistical hypothesis testing is planned.

A complete set of listings containing all documented data and all calculated data (e.g., change from Baseline) will be generated, and will be sorted by site, subject number and visit (where applicable).

## **3.2 General study level definitions**

### **3.2.1 Analysis time points**

#### **3.2.1.1 First and last dose of LCM**

Unless otherwise noted, all references to the first dose of LCM in this SAP refer to the first dose of LCM during SP848 (ie, not the first dose of LCM from the previous study in which study

participants participated prior to SP848 for long-term follow-up study participants). Unless otherwise noted, all references to the last dose of LCM in this SAP refer to the last dose of LCM in the study.

### **3.2.1.2 Relative day**

Relative day will be calculated as the current date minus the date of first dose of LCM plus 1 for days on or after the day of first dose of LCM and prior to or on the day of last LCM dose (e.g., the day of first dose will be Day 1). For days prior to the first dose of LCM (the day prior to first dose will be Day -1), relative day will be calculated as the current date minus the date of first dose of LCM. For days after the last dose of LCM, relative day will be calculated as the current date minus the date of last dose of LCM including a “+” to denote post-treatment days (eg, the day after the last dose will be Day +1). Relative day will not be calculated for partial or missing dates.

### **3.2.2 Study periods**

This study consists of a Treatment Period and a Post-Treatment Period.

#### Treatment Period

This is defined as the period of time from the date of first dose of LCM in SP848 to the latter of the last LCM dose date and the study Termination Visit (ie, Early Termination Visit) date.

The Treatment Period is further broken down into the Titration Period and the Post-Titration Period for direct enrollers:

- Titration Period: defined as the date of the first dose of study medication to the day prior to date of Visit 1 or the date of Early Termination (ET) visit in the situation where a subject discontinues prior to the last visit in the Titration Period.
- Post-Titration Period: defined as the date of Visit 1 to the end of the Treatment Period.

#### Post-Treatment Period

This is defined as the period of time from the day after the end date of the Treatment Period and extending through to the Final Clinic Visit or last contact with the subject.

### **3.2.3 Mapping of assessments performed at Early Termination Visit**

Safety and efficacy assessments at an Early Termination Visit (ETV) that correspond to a scheduled visit will be summarized at the scheduled visit corresponding to the ETV if the assessment was scheduled to occur at that visit. Such assessments will also be considered for Last Visit. Study participants who prematurely discontinue the study will be evaluated based on the data collected at each visit attended. For those study participants the ETV will be mapped to the next scheduled visit, ie, the assessments documented at Visit 13/ETV will be assigned to the next scheduled visit, for which the corresponding assessment is scheduled, following the last documented visit.

In particular, assessments which are done at all visits during the Treatment Period (eg, vital signs, body weight and height), will have ETVs corresponding to a scheduled visit mapped to the corresponding scheduled visit.

For study participants enrolled from sites in Japan, they are allowed to stay in the study longer than 2 years. Such study participants will have a separate ETV if they are in the study after Visit 13.

### 3.2.4 Study visit labeling

Visits will be labeled in table summaries (according to the schedule outlined in Section 16.1 of the protocol) as follows:

- “Screening Visit” for study participants who directly enrolled into SP848
- “Titration Visit X” for scheduled visits during titration for study participants who directly enrolled into SP848
- “Visit X, Week X” for other scheduled visits during the Treatment Period
- “Last Visit” (see below in Section 3.2.6 for further information)

Listings will also include “Unscheduled Visit” as applicable.

### 3.2.5 Monthly time intervals

A month is defined as 28 days and time intervals based on monthly durations are defined as multiples of 28 days (eg, 12 months is defined as 336 days). A subject is included in the analysis for a 3-month interval if they are exposed to LCM at any time during that time interval.

### 3.2.6 Last Visit

The Last Visit for all assessments in SP848 is the last non-missing assessment during the Treatment Period. All scheduled and unscheduled assessments within this time period will be considered. Last Visit will be determined separately for each study procedure where Last Visit is mentioned within this document.

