### **3.3 Definition of Baseline values**

In general, Baseline will be defined as the last non-missing value collected prior to the first dose of LCM in the original study for rollover subjects and in SP848 for direct enrollers for safety and efficacy variables unless otherwise noted for a specific type of data. The Baseline value for seizure counts for directly enrolled study participants will be taken from the Historical Seizure Count CRF/eCRF module collected in SP848 in combination with the seizure diary data collected from the date of the Screening Visit to the day prior to the date of first dose of LCM.

For participants enrolling from EP0060 the baselines for the questionnaires will consider each EP0060 enrollment group separately, those are: ILL (Initiating intravenous lacosamide Group: not currently receiving LCM, i.e. LCM naïve), OLL (Open-label lacosamide Group: currently receiving oral LCM in open-label long term study), and RxL (Prescription lacosamide Group: currently receiving prescribed oral LCM from commercial supply, VIMPAT). For ILL group baseline will be Visit 1 from SP848, for OLL group baseline will come from SP848 using above baseline definition, and for RxL group there will be no baseline data as they were on oral LCM prior to EP0060.

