#### 8.4.2 Electrocardiograms (ECGs)

Standard 12-lead ECGs (2 interpretable recordings [20 to 30 minutes apart]) will be performed throughout the study, according to the tabular schedule of study procedures.

For ECGs, Baseline will be defined as the average of all pre-dose interpretable readings. Assessments with missing time on day of first dose will be assumed pre-dose. For all post-Baseline visits, the average of all interpretable readings at the specified visit will be used for summaries.

Observed values of ECG results will be summarized for each visit and Last Visit. Change from Baseline in ECG results will be summarized for all post-Baseline visits, and Last Visit. This will be summarized overall and repeated by weight band using the levels defined in Section 3.2.10.

The number and percentage of study participants with no abnormality, an abnormal but not clinically significant finding, and a clinically significant finding, will be summarized for all visits, and Last Visit. Percentages will be relative to the number of study participants with an

ECG assessment at each visit. Study participants are counted at most once at each visit based on the worst observed outcome across all abnormalities reported at that visit.

Summaries of shifts from Baseline to post-Baseline visits, and from Baseline to Last Visit will also be provided based on the categories normal, abnormal, not clinically significant, and abnormal, clinically significant.

A listing of ECG data will be provided for all study participants with other significant TEAEs in the Cardiac and ECG Related Terms category defined in Appendix 12.2. A subject data listing of all ECG parameter values for all study participants will also be presented. Listings will include results from each recording and the average of all recordings.

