**Table 8–4: CBCL/6-18**

Syndrome scale	Items
Aggressive behavior	3, 16, 19, 20, 21, 22, 23, 37, 57, 68, 86, 87, 88, 89, 94, 95, 97, 104
Anxious/depressed	14, 29, 30, 31, 32, 33, 35, 45, 50, 52, 71, 91, 112
Attention problems	1, 4, 8, 10, 13, 17, 41, 61, 78, 80
Rule-breaking behavior	2, 26, 28, 39, 43, 63, 67, 72, 73, 81, 82, 90, 96, 99, 101, 105, 106
Social problems	11, 12, 25, 27, 34, 36, 38, 48, 62, 64, 79
Somatic complaints	47, 49, 51, 54, 56a, 56b, 56c, 56d, 56e, 56f, 56g
Thought problems	9, 18, 40, 46, 58, 59, 60, 66, 70, 76, 83, 84, 85, 92, 100
Withdrawn/depressed	5, 42, 65, 69, 75, 102, 103, 111

Standardized T-scores are determined for each subject’s raw syndrome and overall scores based on the subject’s age and sex. Tables mapping each raw score to the appropriate T-score are provided in the CBCL Professional Manual. Standardized T-scores determined from each subject’s raw syndrome scale scores will be reproduced programmatically using the spreadsheets “c15group2-probscales18moto5yrs” and “cbcgrou2-probscales6to18”.

Raw scores and change from Baseline for each CBCL/1½-5 syndrome (aggressive behavior, anxious/depressed, attention problems, emotionally reactive, other problems, sleep problems, somatic complaints, and withdrawn) will be summarized for each visit, and Last Visit.

Raw scores and change from Baseline for each CBCL/6-18 syndrome (aggressive behavior, anxious/depressed, attention problems, rule-breaking behavior, social problems, somatic complaints, thought problems, and withdrawn/depressed) will be summarized for each visit, and Last Visit.

The Calculated T-scores, raw scores, and change from Baseline in raw scores will be listed.

A decrease from Baseline (change from Baseline <0) in the CBCL syndrome raw score will indicate improvement in behavior, while an increase (change from Baseline > 0) indicates worsening.

In addition, for both the CBCL/1½-5 syndrome and /6-18 syndrome, subjects will be categorized according to the Calculated T-score as follows:

- T-score is < 65 = “Normal”
- T-score is ≥ 65 = “Borderline or Clinical range (BCR)”

Summaries of shifts from Baseline to each post-Baseline visit, and from Baseline to Last Visit will also be provided based on the CBCL calculated T-score categories of Normal and BCR. The descriptive summaries of change from Baseline and shift summaries will be presented only when a corresponding Baseline value is available.

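### Last Visit is not required to follow Baseline, so in two entry groups a participant without follow-up can be counted as unchanged

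*SAP*

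**What the plan says.** - **Last Visit (SAP 3.2.6).** Last Visit "is the last non-missing assessment during the Treatment Period. All scheduled and unscheduled assessments within this time period will be considered". It is determined procedure by procedure. No condition ties it to Baseline.
- **Treatment Period (SAP 3.2.2).** It is the "period of time from the date of first dose of LCM in SP848" up to the later of the last dose and the termination visit. It opens on a calendar date, so a value taken that morning before dosing is inside it.
- **Visit labels (SAP 3.2.4).** The numbered-visit label is reserved "for other scheduled visits during the Treatment Period", which places Visit 1 within the period.
- **Baseline (SAP 3.3).** For rollover participants it generally precedes the first LCM dose of the original study. For direct enrollers it is the last value before the first SP848 dose. For questionnaires in EP0060 entrants there is a special rule: "For ILL group baseline will be Visit 1 from SP848". That is the LCM-naive group.
- **ECG (SAP 8.4.2).** Baseline averages all interpretable pre-dose readings, and "Assessments with missing time on day of first dose will be assumed pre-dose".
- **Filter on CBCL summaries (SAP 8.4.8; same rule for BRIEF-P and BRIEF in 8.4.9).** "The descriptive summaries of change from Baseline and shift summaries will be presented only when a corresponding Baseline value is available". For PedsQL (10.3) a change is calculated only when the form matches the one used at Baseline.

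**The concern.** Read together, these rules allow one record to be both the start and the end of a change score. The result is then zero whatever happened to the child, and the shift table files the child under no shift. None of the filters removes the record: a Baseline value exists, and a questionnaire compared with itself is always on the same form.

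In effect this carries Baseline forward for someone with no follow-up. SAP 4.2.1 says missing values are not imputed unless noted, and nothing is noted here. The direction also matters for safety scales: false zeros pull mean change toward zero and fill the unchanged cells, which can hide worsening.

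The outputs concerned are the Last Visit change and shift summaries for CBCL, BRIEF-P, BRIEF and PedsQL (change only), and, for direct enrollers with a Day 1 pre-dose Baseline, those for ECG and other procedures. For the complete neurological examination (8.4.4.1) and Tanner stage (8.4.6), the shift to Last Visit is the only shift table planned.

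**Working it through.** The SAP gives no figure to reproduce on this point; the study is descriptive (3.1). The check applies its date rules to five illustrative participants, with Day 1 as the date of first SP848 dose. The scores are invented.

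**Rule as written:** Last Visit = latest value from Day 1 to the end of the Treatment Period. **Rule with a post-Baseline condition:** the same, but dated after that participant's Baseline.

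| Participant | Values (day: score) | Baseline | Last Visit change, as written | With the condition |
|---|---|---|---|---|
| (a) EP0060 LCM-naive, Visit 1 only | 1: 60 | 60 | 60 − 60 = 0 | none |
| (b) EP0060 LCM-naive, later value | 1: 60; 336: 50 | 60 | 50 − 60 = −10 | −10 |
| (c) Direct enroller, Day 1 pre-dose is the latest value | −7: 62; 1: 60 | 60 | 60 − 60 = 0 | none |
| (d) Direct enroller, Screening only | −7: 62 | 62 | no Last Visit | none |
| (e) Rollover, prior-study Baseline, Visit 1 | −60: 66; 1: 60 | 66 | 60 − 66 = −6 | −6 |

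Only (a) and (c) change. Case (e) is a genuine post-Baseline value and must be kept.

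**ECG.** If the two values in (c) were ECG readings that both entered the average, Baseline would be (62 + 60)/2 = 61 and the Last Visit change 60 − 61 = −1: near zero, not exactly zero.

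**Dilution.** If a share f of the records in a Last Visit table are forced zeros, the mean change is multiplied by (1 − f):

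- f = 1% gives 0.99
- f = 5% gives 0.95
- f = 10% gives 0.90
- f = 20% gives 0.80

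The SAP does not give f.

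**How many could be affected.** SAP 2.5 caps EP0060 entrants at 100 and total enrolment at about 400: 100/400 = 25% of enrolment. Only the LCM-naive part counts, and of those only children with no later questionnaire. The size of that part is not stated. The 25% is a share of enrolment, not a limit for any one age-specific or form-specific table. Direct enrollers number up to about 100 + 46 + 60 = 206, but for them the artefact needs a Day 1 pre-dose value and nothing afterwards.

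**The case against.** The strongest reply is that early leavers usually do have a final value. SAP 3.2.3 counts Early Termination Visit assessments toward Last Visit, and 3.2.2 extends the Treatment Period to that visit. The artefact therefore needs both early departure and no value of that procedure at termination. This stands, and it limits the size.

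A reader might infer that f equals the dropout probability. With an assumed 20% per year, f = 1 − exp(−0.2t) gives 9.5% if the next questionnaire is due at 6 months and 18% at 12 months. For 10% to 30% per year the ranges are 5–14% and 10–26%. The SAP does not support these as estimates. The dropout rate and timings are assumptions, termination assessments are ignored, and the factor would apply within the LCM-naive group, which has no table of its own. If all 100 EP0060 entrants were LCM-naive, within 400 participants and with no termination value, the central figures become 0.25 × 9.5% = 2.4% and 0.25 × 18% = 4.5%.

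A reader might also infer that any Day 1 value is affected. It is not: rollover participants with a prior-study Baseline show a real change. Section 8.4.2 does not say that a Day 1 pre-dose ECG is expected; it says how to treat a Day 1 reading without a time. Treatment-emergent ECG abnormalities already require a post-Baseline visit.

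Finally, these are not the main outputs. The primary safety variables are TEAEs, SAEs and withdrawals due to TEAEs (2.3.1). The questionnaires and ECG are other safety or other efficacy variables, and are also shown by visit. This too stands. None of it supplies the missing condition in 3.2.6.

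**Conclusion.** The gap is real. As written, 3.2.6 lets the Baseline record serve as Last Visit for LCM-naive EP0060 entrants (questionnaires only) and for direct enrollers whose Baseline was taken before dosing on Day 1, when nothing later was recorded. Such participants are reported as unchanged when they were not followed.

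The effect is probably small, and its size cannot be computed from the SAP. The documents do not support a claim that Last Visit results are materially biased overall, or that the study's main safety conclusions are at risk. Summaries at later scheduled visits, TEAE tables and treatment-emergent ECG abnormalities are unaffected.

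The conclusion rests on one assumption: that Visit 1 of EP0060 entrants falls on or after the date of first SP848 dose. Section 3.2.4 implies this, but the visit schedule itself is in the protocol.

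**What to change.** Amend 3.2.6 along these lines: *For each procedure, Last Visit is the latest non-missing post-Baseline value within the Treatment Period, with Baseline as defined for that participant and procedure. A record used to derive Baseline (Section 3.3 or 8.4.2) cannot be Last Visit.*

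Leave participants without such a value out of the Last Visit change and shift summaries, and show their number beside the table.

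Do not exclude a value merely because it precedes the first SP848 dose. For rollover participants that value can be genuinely post-Baseline, as in case (e).

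The cost is a short addition to 3.2.6, one programming condition and a slightly smaller Last Visit n. No genuine follow-up value is lost.
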